### 1 Patient-level Results

For the patient-level portion the response variable is whether the patient developed an infection (i.e. had at least one infected pin). The results are given below in Table 1. The top number in each cell is the number of patients in the given category, and the bottom number is the row percentage. For example, two of the patients in the Control group experienced an infection. This accounts for 33.33% of the patients in the Control group.

A chi-square test is usually appropriate for this type of data, however the chi-square test assumes the expected frequency in each cell is at least 5. This does not hold true for this data set, so Fisher's exact test was run instead. Fisher's exact test has no such expected frequency assumption. The two variables were Group (DuraDerm or Control) and Infection (Yes or No). Based on a  $p$ -value of 0.45, there is not sufficient evidence to suggest there is a significant association between Group and Infection.

Table 1: Patient infection outcomes

Group	Infection		
	Yes	No	Total
DuraDerm	0	6	6
	0%	100%	
Control	2	4	6
	33%	67%	
Total	2	10	12

Table 2: Pin infection outcomes

Group	Infection		
	Yes	No	Total
DuraDerm	0	60	60
	0%	100%	
Control	14	46	60
	23%	77%	
Total	14	106	120

Note that an *a priori* power analysis indicated that the minimum sample size required to achieve 80% power was 33 patients per group. Due to a lack of 66 available patients, this portion of the analysis is severely under-powered. However, from a descriptive standpoint the results were in line with the values that went into the power analysis. So if the observed trend continued with the appropriate sample size, it would become statistically significant.

## 2 Pin-level Results

These studies are reported in the literature at both the patient-level and the pin-level. After consultation with your surgeon it was determined that there is consensus in the orthopedic surgical community that the pins can be treated as independent. Therefore, for the pin-level portion of the analysis the response variable is whether the individual pin site became infected. The results are given above in Table 2.

For this portion of the analysis the chi-square test is appropriate because all of the expected counts are at least five. Do not confuse expected counts with observed counts. The observed count of infections for the DuraDerm group is zero, however the expected count is the column total multiplied by the row total and divided by the total sample size. So for this cell the expected count

would be  $(14 * 60 / 120) = 7$ .

The same two variables were used (Group and Infection), except now they refer to the individual pins instead of the patients. Based on a *p*-value of <0.0001, there is strong evidence to suggest there is a significant association between Group and Infection.

One way to quantify this association is in terms of a risk ratio, which is a ratio of the risks of infection for the two groups. The estimated risk ratio for this data set is 0.03. This means that a pin that receives DuraDerm is 0.03 times as likely to become infected as a pin that does not receive DuraDerm. Another way of saying this is the risk of a pin becoming infected is 97% lower for the DuraDerm group compared to the Control group. A 95% confidence interval for the true risk ratio is (0.002, 0.57). So while the observed risk ratio was 0.03, it could feasibly be as high as 0.57.

Let me know if you have any questions about anything contained in this report or related to this research in general. I have enjoyed collaborating with you on this project and hope you consider Wright State University's Statistical Consulting Center for future research.

Sincerely,  
[name]

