**DuraDerm® should be reapplied at the end of each Pin Care Cleaning Regimen.**

**See Attachment – Schedule of Events**

### **Data Analysis and Data Monitoring**

This is a prospective observational case series study to measure the potential reduction in pin track infection rate among research participants undergoing Deformity Correction and Traumatic Provisional Fixation.

Data will be collected by clinical staff under supervisor of the Principal Investigator. Data collected is primarily categorical and will be analyzed using tabulations (tables of frequencies), visual displays (histograms), and chi-square or Fisher exact tests to measure variable independence (e.g., infection rate based on age, number of pins/research participants, etc.).

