### **Research participant Identification, Recruitment and Consent Form**

### **Method of Research Participant Identification, Recruitment and Consent/Assent**

Research participants identified for the study will be those undergoing Deformity Correction and Traumatic Provisional Fixation who are under the care of the Primary Investigator. These research participants have a number of pins placed to ensure this required rigid fixation. The number of external fixation pins averages approximately ten per research participant. Research participants seen by the Primary Investigator who will be undergoing deformity correction or traumatic provisional fixation, will be invited to take part in this research study. No recruitment of the Principal Investigator's own students, employees, or family members will be allowed. Research participants who do not wish to participate in this randomized study will be provided the standard pin track care protocol this investigator utilizes for his research participants and will not have the opportunity to receive DuraDerm®.

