## Final Report for DuraDerm Data Analysis

December 23, 2019

Here are the results of the analysis of your DuraDerm data. You are interested in determining whether patients undergoing orthopedic reconstructive or repair surgery for deformity correction or trauma who have an external fixation held in place by metal pins experience lower infection rates when DuraDerm is applied to the pin site than patients who receive no DuraDerm (Control). The data set consists of twelve patients who each had, on average, ten pins holding the external fixation in place. Six of the patients were randomly selected to receive a DuraDerm application while the other six patients received no DuraDerm. Both groups of patients received standard pin track care. You would like to answer this question from both the patient-level perspective and the pin-level perspective. A level of significance of  $\alpha = 0.05$  was used throughout. SAS version 9.4 (SAS Institute, Inc., Cary, NC) was used for all analyses. Descriptive statistics for the patient demographics are provided in the appendix.

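### The pin-level test treats 120 pins as independent although all 14 infected pins came from 2 patients, so its p<0.0001 and risk-ratio interval are invalid; the patient-level result is inconclusive

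*SAP*

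**What the plan says.** The SAP document is a final analysis report. Its introduction describes "twelve patients who each had, on average, ten pins" and gives the allocation: "Six of the patients were randomly selected to receive a DuraDerm application while the other six patients received no DuraDerm". The patient is therefore the unit that received or did not receive the product.

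Section 1 (Patient-level Results) defines an infected patient as one with at least one infected pin and reports that "two of the patients in the Control group experienced an infection". No DuraDerm patient did (Table 1). Fisher's exact test gives p = 0.45, and the report calls this analysis severely under-powered.

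Section 2 (Pin-level Results) states, after consultation with the surgeon, that "there is consensus in the orthopedic surgical community that the pins can be treated as independent". It applies a chi-square test to Table 2 (0 of 60 DuraDerm pins and 14 of 60 Control pins infected), obtains p<0.0001 and concludes that "there is strong evidence to suggest there is a significant association between Group and Infection". It adds a risk ratio of 0.03 with a 95% interval of 0.002 to 0.57, and describes the risk as 97% lower.

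The Protocol (Data Analysis and Data Monitoring) plans tabulations, histograms and chi-square or Fisher tests. It does not mention pins nested within patients.

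**The concern.** Pins in one limb share a patient, a wound environment, a caregiver and a cleaning routine. A test that counts them as separate observations overstates the information unless infections really do occur independently from pin to pin. The report supports that assumption only by a reported consensus, and justifies the chi-square test only by the expected cell counts, which say nothing about independence.

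This decides the report's conclusion. The pin-level analysis supplies its only significant p-value and its only confidence interval. Without them, what remains is a comparison of six patients with six, which cannot settle the question in either direction.

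**Working it through.** **1. Reproducing the report.**
- Pin-level Pearson chi-square, no continuity correction: 120 × (0×46 − 60×14)² / (60×60×14×106) = 15.85, p = 6.9 × 10⁻⁵. The report gives <0.0001.
- Pin-level risk ratio with 0.5 added to each cell: 0.5/61 divided by 14.5/61 = 0.034. The standard error of its log is the square root of 1/0.5 plus 1/14.5 minus 2/61, which is 1.427, so the 95% interval is 0.0021 to 0.565. The report gives 0.03 with interval 0.002 to 0.57.
- Patient-level Fisher test, 0/6 against 2/6: the chance that both infected patients fall in Control is C(6,2)/C(12,2) = 15/66. Two-sided, 30/66 = 0.4545. The report gives 0.45.

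The arithmetic is right. The unit of analysis is not.

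**2. Where the 14 infected pins lie.** A patient counts as infected with one or more infected pins. Only two Control patients qualify, so they carry all 14 infected pins and the other four Control patients carry none. This needs no assumption about pin counts.

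**3. Is that compatible with independence?** Given 14 infected among 60 independent Control pins, the chance that they fall in at most two of six patients depends on the pin counts, which the report gives only as an average of ten:

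| Pins in the six Control patients | Probability |
|---|---|
| 10 each | 15 × C(20,14)/C(60,14) = 3.4 × 10⁻⁸ |
| two with 14 and four with 8 | 2.5 × 10⁻⁶ |
| two with 20 and four with 5 | 0.0013 |

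For the two infected patients specifically, C(m,14)/C(60,14) first exceeds 0.05 when together they hold m = 50 of the 60 pins.

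**4. Patient-level estimates.**
- Risk ratio by the report's own method: 0.5/7 divided by 2.5/7 = 0.20. The standard error of its log is the square root of 1/0.5 plus 1/2.5 minus 2/7, which is 1.454, giving 0.01 to 3.5.
- Risk difference, Control minus DuraDerm: 2/6 minus 0/6 = 33 points. The Wilson limits are 0.097 to 0.700 for 2/6 and 0 to 0.390 for 0/6. The lower Newcombe limit is 0.333 − √(0.236² + 0.390²) = −0.12. The upper limit is 0.333 plus 0.367 = 0.70, where 0.367 is 0.700 less 0.333.
- With two infected patients in a 6:6 split the only attainable two-sided Fisher p-values are 0.4545 and 1. With 0/6 on DuraDerm, 4/6 in Control would give 0.061 and 5/6 would give 0.015.

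**5. A pin-based test that respects allocation.** Permute whole patients over the C(12,6) = 924 allocations, taking the difference between arms in total infected pins as the statistic. For every split of the 14 pins from 7/7 to 13/1, 420 allocations are at least as extreme: 420/924 = 0.4545. This is the Fisher calculation again and not separate corroboration.

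**6. Illustrative size of the clustering.** Assume ten pins each and a 7/7 split, and use the within-arm ANOVA estimate. The between-patient mean square is 6.533/10 = 0.653 and the within-patient mean square is 4.2/108 = 0.039; their difference is 0.614. The intracluster correlation is 0.614 divided by (0.653 + 9 × 0.039) = 0.61, the design effect is 1 + 9 × 0.61 = 6.5, and the adjusted chi-square is 15.85 divided by 6.51 = 2.43, p = 0.12. A 10/4 split gives correlation 0.79, design effect 8.1 and p = 0.16.

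**7. False-positive rate.** I simulated no treatment effect with ten pins each, a patient infection risk of 17% to 33%, and 30% to 70% of pins infected in an infected patient (these rates are assumptions). The pin-level chi-square rejects in 29% to 55% of trials against a nominal 5%.

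**The case against.** The report is open about what it did. It states the independence assumption, puts the patient-level result first and says that 33 patients per group were needed for 80% power. Pin-level rates are also a legitimate description: the Protocol's Background cites a 27% literature rate defined for a random pin or wire site. All of this stands, and the criticism is confined to the inference. Disclosing an assumption does not rescue it when the adjacent table contradicts it, and counting pins does not replace missing patients.

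The design-effect figures depend on unknown pin counts. With a 7/7 split and ten pins per DuraDerm patient, the adjusted p is about 0.044 to 0.051 if the two infected patients had 14 pins each, 0.022 to 0.033 with 16 each, and 0.003 to 0.008 with 20 each, according to the mean cluster size used. The adjustment therefore does not show that significance is lost in every layout, although all these values are far above the reported one. The approximation is also rough with 12 patients. The conclusion does not rest on it.

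The simulation applies the chi-square to every dataset. Limited to tables meeting the report's own expected-count rule (at least 10 infected pins in total), the error rate is 28% to 46%, still far above 5%.

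Finally, clustering alone is not a reason to drop a crude point estimate. The reason to drop 0.03 and the 97% reduction is that they come from the 0.5 added to each cell: the observed ratio is 0/14, that is, zero.

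**Conclusion.** The concern holds. Allocation by patient, together with all 14 infected pins lying in two patients, makes the pin-level p<0.0001 and the interval 0.002 to 0.57 invalid as evidence of a treatment effect. Both facts come from the report itself and need no assumption about pins per patient. The design-effect and simulation figures are illustrative.

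The valid comparison is 0/6 against 2/6 infected patients: p = 0.45, risk difference 33 points (−12 to +70). It is compatible with a large benefit or with harm. It does not show absence of effect, since no smaller two-sided p was attainable with two infected patients. Reading the p-value as a randomisation result relies on the SAP's statement that patients were randomly selected.

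This must be fixed, because the report's only positive inferential conclusion depends on the error.

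**What to change.** Base the treatment inference on the patient-level Fisher test already reported. In section 2, withdraw the pin-level p-value, the risk ratio of 0.03 with its interval, and the 97% statement. Delete the sentence on independence and the strong-evidence conclusion. Suggested text:

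> Infection occurred in 0/6 DuraDerm and 2/6 Control patients (Fisher p = 0.45, the smallest value attainable with two infected patients; risk difference 33 points, approximate Newcombe 95% CI −12 to +70). The result is inconclusive. Infected pins (0/60 v 14/60) are descriptive only; all 14 came from two patients.

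Add a listing of pins and infected pins per patient. If a pin-based test is wanted, use the whole-patient permutation test with total infected pins as the named statistic, and say that it repeats the Fisher result. The pooled pin rate is unsuitable as the statistic, because its permutation p changes with unequal pin counts.

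Also state how patients were allocated. Under Data Analysis and Data Monitoring the Protocol says "This is a prospective observational case series study", while its recruitment section refers to "Research participants who do not wish to participate in this randomized study" and the SAP says patients were randomly selected.

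The cost is a re-analysis of data already held and new wording. The favourable p-value is lost.
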